2.1 Study Design

This is a prospective, single-arm, multi-center study in islet transplantation. The centers participating in this phase 3 study will also undertake separate, phase 2 studies in islet transplantation, using innovative manufacturing and/or immunosuppressive regimens. In order to avoid bias in selection of subjects for these studies, eligible subjects will be randomized, prior to transplantation, to participate either in the phase 3 or a site-specific phase 2 study. The participating centers will treat a total of 48 study subjects accrued over 24 months in this phase 3 study.

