observe a rate larger than 70%. With a sample size of 48 transplanted subjects, 31 subjects (65%) would need to achieve a favorable outcome for the exact 95% lower confidence bound to rule out a 50% or lower true rate. (This result is not shown in the table; 65% favorable outcome rate of 48 subjects transplanted results in 31 successfully transplanted subjects). The proposed sample size is 48 subjects. Each participating center is expected to enroll at least 6 subjects.

Table 3 displays the probability that the study would conclude that the true favorable outcome rate is at least 50% for several selected values of the true favorable outcome rate. The tabulated probabilities are the power that a one-sided binomial test of the null hypothesis $H_0: p < 0.5$ versus the alternative hypothesis $H_a: p \geq 0.5$ would conclude that the true favorable outcome rate is at least 50% given that the selected value is the true underlying favorable outcome rate. These values are obtained by calculating the binomial probability that at least 31 out of 48 total enrolled subjects would achieve the favorable outcome given the true outcome rate.

Table 3- The power to rule out a favorable outcome rate that is less than or equal to 50% for the given true favorable outcome rate.

True Favorable Outcome Rate	Power to Rule Out Favorable Outcome Rate
10%	0.0000
20%	0.0000
30%	0.0000
40%	0.0005
50%	0.0297
60%	0.3111
70%	0.8359
80%	0.9962
90%	1.0000

This table shows that if the true favorable outcome rate is 70%, the power of concluding that the rate is over 50% is 0.8359 for a 5% level test.

3. General Analysis Definitions

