3.7 Efficacy Analyses

3.7.1 Statistical Analysis of Primary Endpoint

HbA1c is the standard measure of glucose control and is used in all major studies as an endpoint for glycemic control. It has been valuable as a risk predictor of diabetes complications. However, since HbA1c is an integrated average, it does not provide information about the range of glucose values a subject experiences. This limitation is a rationale for also including hypoglycemic event occurrence as part of the primary endpoint and various glycemic excursion measures as secondary endpoints.

The primary endpoint for this study is the proportion of subjects with an HbA1c <7.0% at Day 365 AND free of severe hypoglycemic events from Day 28 to Day 365, inclusive, following the first islet transplant, with the day of transplant designated Day 0.

The primary analysis is designed to estimate the true rate of favorable outcomes at one year in subjects in the ITT population pooled over all centers. The proportion of favorable outcomes will be used as the point estimate. An exact one-sided 95% confidence interval will be constructed assuming an underlying binomial distribution for the target population as follows:

If r out of 48 total enrolled subjects achieve the favorable outcome, the exact one-sided 95% confidence interval is given by $p \geq p_L$ where p_L is the solution of the equation

$$0.05 = \sum_{x \geq r} \binom{48}{x} p_L^x (1 - p_L)^{48-x}.$$

0.05 =

The rates of favorable outcome and exact one-sided 95% confidence intervals will be computed for each contributing center.

This analysis will be conducted for the ITT population. The primary endpoint should be available for all treated subjects. An exception will be if a death occurs, if the subject withdraws consent to be followed, or if immunosuppression is begun but the subject never receives a transplant. In these cases the endpoint will be classified as failure to achieve a favorable outcome. Should the endpoint not be evaluated for a particular individual for other reasons, a failure will be imputed unless an evaluation is done at a time longer than one year after transplant, in which case, that later value will be imputed. All imputations will be reported with the primary analysis. The rates and the exact one-sided 95% confidence intervals for complete data and imputed data will be compared to ascertain the sensitivity of the imputation.

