3.9.4.4 Analysis for Hypoglycemia Fear Scale

3.9.4.4.1 *Analysis at 75 ± 5 days following the initial and final islet transplant*

Obtain the HFS at 75 ± 5 days following the initial and final islet transplant (if applicable). We calculate the sample mean and construct the 95% confidence interval of the mean HFS using the method for a continuous variable described in SAP section 3.6.3.

3.9.4.4.2 *Analysis at 365 ± 14 days following the initial and final islet transplant*

Obtain the HFS at 365 ± 14 days following the initial and final islet transplant (if applicable). We calculate the sample mean and construct the 95% confidence interval of the mean HFS using the method for a continuous variable described in SAP section 3.6.3.

3.9.4.4.3 *Comparison of HFS at three time points*

For each subject, we obtain his/her HFS at baseline, 75 ± 5 and 365 ± 14 days following the initial islet transplant. We compare the difference at the three time points for HFS using the analysis of variance method described in SAP section 3.9.4.1.3.

4. Interim Analyses and Safety Monitoring Analyses

The DSMB will be convened to review safety and efficacy data following National Institutes of Health (NIH) policy. When requested, formal interim analyses to assess safety and efficacy will be performed. Formal interim analyses will include distributions of endpoints, biomarkers and AEs. Additional analyses may be requested by the DSMB.

4.1 *Interim Analysis for Early Stopping*

This is a relatively small study; therefore, there is a need to collect as much safety data as possible, we do not plan to stop early for efficacy. We will monitor for lack of efficacy; the stopping rule will be based on excluding favorable outcome rates less than or equal to 30%.

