The following table provides information on the study's strategy for stopping when the favorable outcome rate is too low. We will use the Lan and Demets [12] error spending approach with the O'Brien-Fleming [13] spending function. These calculations are based on using the O'Brien-Fleming spending function to calculate boundary values for a one-sided test of the hypothesis that the proportion achieving favorable outcome is no lower than a selected minimum value. The calculations assumed a conservative 2.5% level for the overall type I error. The procedure recommends terminating enrollment when there is overwhelming evidence that the favorable outcome rate is unacceptably low. Table 10 provides stopping boundaries for 20%, 30%, and 40% and for 3 and 4 planned analyses. It displays the numbers of favorable outcomes that would result in concluding that the true favorable outcome rate is less than the minimally acceptable rate.

For example, for three analyses and if the lowest acceptable favorable outcome rate were 20%, then the rule could not recommend stopping at the first interim analysis. It would recommend stopping at the second interim analysis (after 32 subjects had completed their one-year follow up) if none of the 32 subjects experienced a favorable outcome. The study would conclude that the favorable outcome rate was less than 20% at the end of the trial if 4 or fewer subjects experienced a favorable outcome. If the lowest acceptable favorable outcome rate were 30%, then the rule would recommend stopping at the second interim analysis if 3 or fewer subjects experienced a favorable outcome. It would conclude that the true favorable outcome rate was less than 30% after 48 subjects had completed the study if 8 or fewer subjects experienced a favorable outcome.

Table 10-Stopping Boundaries for Unacceptable Low Favorable Outcome Rates

Number of Interim Analyses	Interim Analysis	Number of Subjects	Minimally Acceptable Favorable Outcome Rate		
			20%	30%	40%
			Number Experiencing Favorable Outcome To Recommend Stopping		
3	1	16	--	--	--
	2	32	0	≤3	≤6
	3	48	≤4	≤8	≤12
4	1	12	--	--	--
	2	24	--	0	≤2
	3	36	≤1	≤4	≤7
	4	48	≤3	≤7	≤12

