The Lan and Demets spending function approach allows for scheduling interim analysis as needed or requested by NIH or the DSMB. We anticipate that we will need to perform 4 interim analyses. For 4 equally spaced analyses, the stopping rule would not recommend stopping until 24 subjects have completed their one-year follow-up. At that time the rule would recommend stopping if there have been no favorable outcomes. After 36 subjects have completed their one-year follow-up the rule would recommend stopping if fewer than 5 subjects have experienced a favorable outcome. The final efficacy analysis will be adjusted to reflect the “alpha that has been spent” for these interim analyses by adjusting the confidence coefficient for the one-sided exact confidence interval for the primary outcome.

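### Section 4.1 adjusts the final primary confidence level for alpha that lack-of-efficacy looks do not spend, by an unstated amount, which leaves the pass mark at either 31 or 32 of 48

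*SAP*

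**What the plan says.** Section 3.7.1 fixes the primary analysis: "An exact one-sided 95% confidence interval will be constructed assuming an underlying binomial distribution", with 0.05 written into the equation for the lower bound and 48 as the denominator. Section 2.4 derives the success rule from that level: "31 subjects (65%) would need to achieve a favorable outcome for the exact 95% lower confidence bound" to exclude a true rate of 50% or lower. Table 3 rests on the same rule, and section 2.4 concludes that, at a true rate of 70%, "the power of concluding that the rate is over 50% is 0.8359 for a 5% level test". The center evaluation in section 3.7.2.1.3 and Appendix 8.1 also describes the primary analysis as a one-sided 95% interval (criterion a).

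Section 4.1 says of the interim looks that "we do not plan to stop early for efficacy". Monitoring is for lack of efficacy only, against a 30% rate, with O'Brien-Fleming spending at an overall one-sided level of 2.5%. Four equally spaced analyses are anticipated. Under Table 10 the 30% rule has no boundary at 12 subjects, stops at 0 of 24, and stops at 4 or fewer of 36.

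The last sentence of section 4.1 then says that the final efficacy analysis will reflect alpha spent at these looks, "by adjusting the confidence coefficient for the one-sided exact confidence interval for the primary outcome". It gives no adjusted value and no formula.

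**The concern.** A look that can only stop the trial for a low rate removes paths through the trial and cannot add a path to a positive result. It cannot raise the chance of wrongly ruling out 50%, so the final analysis has nothing to repay. The 2.5% spent in section 4.1 belongs to a different hypothesis, that the rate is no lower than 30%, tested in the opposite direction.

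The sentence also leaves the SAP with two descriptions of its only confirmatory test: a fixed 95% interval in sections 2.4 and 3.7.1, and an interval at some other level in section 4.1. A result of exactly 31 of 48 could pass under one and fail under the other. Because the amount is open, the pass mark could be settled after the count is known.

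**Working it through.** **Inputs.** N = 48, null rate 0.50, one-sided alpha 0.05 and critical count 31 (sections 2.4 and 3.7.1). Stopping boundaries for the 30% rule with four analyses: none at 12, 0 of 24, 4 or fewer of 36 (Table 10). Spending level 0.025 (section 4.1).

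**1. The plan's own figures.** With X binomial on 48 subjects:
- P(X ≥ 31 | 0.5) = 0.0297 and P(X ≥ 30 | 0.5) = 0.0557, so 31 is the smallest count that passes at 0.05.
- P(X ≥ 31 | 0.7) = 0.8359 and P(X ≥ 31 | 0.6) = 0.3111.

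These agree with Table 3.

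**2. Effect of the looks.** A trial stopped at 24 with no successes could have reached at most 0 + 24 = 24. A trial stopped at 36 with at most 4 successes could have reached at most 4 + 12 = 16. Neither could have reached 31, so stopping removes no outcome that counts as success. The exact sequential calculation with both boundaries applied gives:
- at a true rate of 50%: probability of stopping about 0.000001, probability of a positive result 0.0297;
- at a true rate of 70%: probability of a positive result 0.8359.

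Both are unchanged. The three-analysis version (3 or fewer of 32) gives the same two figures.

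**3. What the adjustment could mean.** The result at 31 of 48 has p = 0.0297. The pass mark therefore moves to 32 if the final alpha falls below 0.0297, that is, if the confidence coefficient rises above 1 − 0.0297 = 97.03%. Cumulative spending under the Lan-DeMets O'Brien-Fleming function is 2[1 − Φ(z(1−α/2)/√t)]. At t = 0.75 this is 0.0096 for α = 0.025 and 0.0236 for α = 0.05. The chance of crossing 0 of 24 or 4 or fewer of 36 at a true rate of 30% is 0.0002 + 0.0070 = 0.0072.

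| Reading of the sentence | Final alpha | Pass mark |
|---|---|---|
| 0.05 less the exact crossing probability at 30% (0.0072) | 0.0428 | 31 |
| Final nominal level of a 5% four-look plan | about 0.0425 | 31 |
| 0.05 less spend of the 2.5% plan through look 3 (0.0096) | 0.0404 | 31 |
| 0.05 less spend of a 5% plan through look 3 (0.0236) | 0.0264 | 32 |
| 0.05 less the full 2.5% | 0.025 | 32 |
| Final nominal level of the 2.5% four-look plan | about 0.022 | 32 |

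**4. What a pass mark of 32 costs.** P(X ≥ 32 | 0.5) = 0.0147.

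| True rate | Power at ≥ 31 | Power at ≥ 32 | Loss |
|---|---|---|---|
| 60% | 0.3111 | 0.2144 | 0.0967 |
| 70% | 0.8359 | 0.7495 | 0.0864 |
| 75% | 0.9626 | 0.9296 | 0.0330 |

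The loss is the probability of observing exactly 31 successes.

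**The case against.** The strongest reply is that the sentence is harmless. Any upward adjustment of the confidence coefficient is conservative and cannot create a false positive. Read literally, alpha already spent before the final look is 0.0096 or less under the 2.5% plan, and subtracting it from 0.05 leaves the rule at 31 of 48 and Table 3 intact. Even with 32 needed, power is 0.93 at a 75% rate, and the historical rate in Table 1 is 76%.

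All of this is correct, and it limits the size of the point. A reader might infer that section 4.1 does cut power to 0.75. The SAP does not support that, because the loss arises only under some readings. The reply does not explain why an adjustment is needed, however, and it does not settle which reading applies.

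A reader might also infer that the looks are useless because, on a crossing, "The procedure recommends terminating enrollment when there is overwhelming evidence that the favorable outcome rate is unacceptably low", and 24 one-year completers come too late to affect enrollment. Section 2.1 gives 48 subjects over 24 months but no accrual pattern. At an assumed even 2 per month, the 24th subject completes at month 12 + 12 = 24, just as enrollment ends. Under an assumed front-loaded pattern that look falls near month 18 with about 42 of 48 enrolled. Section 4.1 also allows looks on request, and section 4.2 describes separate suspension reviews. The documents therefore do not show that the looks cannot stop enrollment or that they protect nobody. The leniency of the 30% rule is a design choice, for which section 4.1 gives the need for safety data as its reason.

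**Conclusion.** The adjustment is unwarranted, unspecified, and inconsistent with sections 2.4 and 3.7.1. That the looks spend no alpha on the test of 50% rests only on the boundaries in Table 10 and the absence of an efficacy boundary. It holds whether or not a stopping recommendation is followed.

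The practical effect is an undefined pass mark. It is 31 of 48 if the final alpha is about 0.040 to 0.043, with no loss. It is 32 of 48 if the final alpha is below 0.0297, with power down from 0.836 to 0.749 at a 70% rate and from 0.311 to 0.214 at 60%. These figures assume exactly 48 subjects in the analysis, as section 3.7.1 does. The point concerns the final interval only and makes no finding on the futility rule itself.

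**What to change.** Delete the last sentence of section 4.1. In its place, state that the interim looks can stop only for lack of efficacy, that they spend no alpha on the primary test, and that the final analysis uses the unadjusted exact one-sided 95% bound of section 3.7.1, that is, at least 31 of 48.

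The cost is a wording change in the SAP. Type I error stays at 0.0297, Table 3 stands as printed, and criterion (a) of the center evaluation again matches the primary analysis.

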4.2 Safety Monitoring Analyses

AEs and clinical outcomes are monitored closely in this study. To protect the safety of subjects, safety stopping rules for the protocol and individuals sites have been developed.

4.2.1 Protocol Suspension and Review

Criteria for protocol suspension and review are detailed in the CIT-07 protocol, section 6.2.1.

After the protocol is placed on hold, no additional transplants within the trial will be performed at any participating clinical site until the CIT Steering Committee and DSMB meet either in person or by conference call to review in depth the results and circumstances surrounding the islet functional failure or SAE to determine whether the trial enrollment of new subjects and conduct of additional transplants could be safely resumed.

4.2.2 Site Suspension and Review

Criteria for suspension of study enrollment and initial islet infusions at individual sites are detailed in the CIT-07 protocol, section 6.2.2.

After any site is placed on hold, no additional transplants will be performed at that site until the CIT Steering Committee and DSMB meet either in person or by conference call to review in depth the results and circumstances surrounding the islet functional failure or SAE to determine whether the trial enrollment of new subjects and conduct of additional transplants could be safely resumed at that site, or whether there could be implications for the continuation of the entire proposed pilot protocol also at other affiliated sites testing the same protocol.

In all cases of PNF, subjects will be asked to temporarily continue immunosuppression to decrease the risk of sensitization that could increase the risk of poor outcome should future transplants occur. A tapering schedule will be applied until immunosuppressants are completely discontinued.

Reference

- [7] Steja D. Can continuous glucose monitoring provide objective documentation of hypoglycemia unawareness? *Endocr Pract.* 2005; 11(2):83-90.

Appendix 1 - Descriptive Statistics of Baseline Data

	Center						Total
	Univ Of Alberta	Univ of Miami	Univ of Minnesota	Univ Of Pennsylvania	Emory Univ	Northwestern Univ	
Demographic Variables							
n							
mean							
s.d.							
median							
range							
Sex: n (%)							
1. male							
2. female							
3. total							
Race: n (%)							
1. White							
2. Black							
3. Hispanic							
4. Asian							
5. Other							
Disease Factors							
Insulin Req.							
n							
mean							
s.d.							
median							
range							
HbA1c							
n							
mean							
s.d.							
median							
range							
# of Severe Hypo.							
n							
mean							
s.d.							
median							
range							
MAGE							
n							
mean							
s.d.							
median							

range							
LI n mean s.d. median range							
Clarke Score n mean s.d. median range							
HYPO score n mean s.d. median range							
β -score n mean s.d. median range							
C-peptide glucose Creatinine Ratio n mean s.d. median range							
Physical Conditions							
Body Weight n mean s.d. median range							
Height n mean s.d. median range							
QOL 1. SPC n mean s.d. median range 2. SMC n							

mean							
s.d.							
median							
range							
3. OHS							
n							
mean							
s.d.							
median							
range							
4. DDS							
n							
mean							
s.d.							
median							
range							
5. HFS							
n							
mean							
s.d.							
median							
range							

Appendix 2 - Summary Table of Adverse Events Related to the Islet transplant and Immunosuppression Therapy

Events	Degrees of Event Severity					Total
	Grade 1	Grade 2	Grade 3	Grade 4	Grade 5	
AE related to the islet transplantation (islet product or islet transplant procedure):						
AE-IIP-1 Number (%) Resolved? Number (%) mean s.d. median min-max						
AE-IIP-2 Number (%) Resolved? Number (%) mean s.d. median min-max						
AE-IIP-3 Number (%) Resolved? Number (%) mean s.d. median min-max						
AE-IIP-4 Number (%) Resolved? Number (%) mean s.d. median min-max						
AE-IIP-5 Number (%) Resolved? Number (%) mean s.d. median min-max						
AE related to the immunosuppression and/or infection prophylaxis:						
AE-IP-1 Number (%) Resolved? Number (%) mean s.d.						

median min-max AE-IP-2 Number (%) Resolved? Number (%) mean s.d. median min-max AE-IP-3 Number (%) Resolved? Number (%) mean s.d. median min-max AE-IP-4 Number (%) Resolved? Number (%) mean s.d. median min-max AE-IP-5 Number (%) Resolved? Number (%) mean s.d. median min-max AE-IP-6 Number (%) Resolved? Number (%) mean s.d. median min-max AE-IP-7 Number (%) Resolved? Number (%) mean s.d. median min-max AE-IP-8 Number (%) Resolved? Number (%)						
--	--	--	--	--	--	--

mean s.d. median min-max AE-IP-9 Number (%) Resolved? Number (%) mean s.d. median min-max AE-IP-10 Number (%) Resolved? Number (%) mean s.d. median min-max AE-IP-11 Number (%) Resolved? Number (%) mean s.d. median min-max						
---	--	--	--	--	--	--

**Appendix 3 - Adverse Events: Number Observed and Rate with Patient
Identifications Grouped by Severity and Attribution**

Events	Degrees of Event Severity					Total
	Grade 1	Grade 2	Grade 3	Grade 4	Grade 5	
AE related to the islet transplantation (islet product or islet transplant procedure):						
AE-IIP-1 incidences	6 (12.5%) C11+ C12 C22 C34 C63 C66					
AE-IIP-2 incidences						
AE-IIP-3 incidences						
AE-IIP-4 incidences						
AE-IIP-5 incidences						
AE related to the immunosuppression and/or infection prophylaxis:						
AE-IP-1 incidences						
AE-IP-2 incidences						
AE-IP-3 incidences						
AE-IP-4 incidences						
AE-IP-5 incidences						
AE-IP-6						

incidences						
AE-IP-7 incidences						
AE-IP-8 incidences						
AE-IP-9 incidences						
AE-IP-10 incidences						
AE-IP-11 incidences						

+ : Patient's identification, for example C11 stands for the incidence occurring on patient number 1 at Center #1

Appendix 4 - Analysis of Adverse Events at Month # since the Randomization

	AE related to the islet transplantation (islet product or islet transplant procedure) or immunosuppression and/or infection prophylaxis			AE not related to the islet transplantation (islet product or islet transplant procedure) or immunosuppression and/or infection prophylaxis		
All Adverse Events	# of incidences	The incidence rate per 100 person- days (λ)	The 95 % confidence interval of λ based on MLE theory	# of incidences	The incidence rate per 100 person- days(λ)	The 95 % confidence interval of λ based on MLE theory
Body System A 1. Grade 5 2. Grade 4 Event 1 Event 2 ⋮ 3. Grade 3 Event 1 Event 2 ⋮ 4. Grade 2 Event 1 Event 2 ⋮ 5. Grade 1 Event 1 Event 2 ⋮						
Body System B 1. Grade 5 2. Grade 4 Event 1 Event 2 ⋮ 3. Grade 3 Event 1 Event 2 ⋮ 4. Grade 2 Event 1 Event 2 ⋮ 5. Grade 1 Event 1						

Event 2 ⋮						
Body System C 1. Grade 5 2. Grade 4 Event 1 Event 2 ⋮ 3. Grade 3 Event 1 Event 2 ⋮ 4. Grade 2 Event 1 Event 2 ⋮ 5. Grade 1 Event 1 Event 2 ⋮						
⋮						

